## 1.3.2. Visits on Day 1 of Every Other Cycle (up to 35 cycles and >35 cycles)

Visit Identifier	Visits on Day 1 of Every Other Cycle up to 35 cycles (up to 24 months)	Visits on Day 1 of Every Other Cycle (> 35 cycles or 24 months)	Notes  (X) refer to specific footnote when the measurement may be optional /repeat measurement might not be required.
Visit Window	±4 days	±4 days	
Physical examination	X		
Weight	X		
Contraception check (as	X	X	At cycle not requiring site visit the participant may be contacted by phone to
appropriate)	(every cycle ±2 days)	(every cycle ±2 days)	confirm contraception is still appropriate per the protocol.
Laboratory			

Visit Identifier	Visits on Day 1 of Every Other Cycle up to 35 cycles (up to 24 months)	Visits on Day 1 of Every Other Cycle (> 35 cycles or 24 months)	Notes  (X) refer to specific footnote when the measurement may be optional /repeat measurement might not be required.
Visit Window	±4 days	±4 days	
Pregnancy test	X (every cycle ±2 days)	X (every cycle ±2 days)	Pregnancy tests will be routinely repeated at every cycle (±2 days) during the active treatment period and additionally whenever one menstrual cycle is missed or when potential pregnancy is otherwise suspected. The pregnancy test should be performed at the clinical site's local laboratory. Where that is not possible, participants will provide the laboratory test results carried out at a non-clinical site laboratory, eg, by telephone, and bring a copy of the laboratory test results at the next cycle visit. The copy of the laboratory test results must be retained in the participants' file at the clinical site for documentation purposes.
Study Intervention			
Study Intervention	Once a day continuously		
Tumor Assessments			
CT and MRI Scan or Equivalent	(every 6 weeks ± 1 week)	(As per local clinical practice)	CT and MRI scans to be done at every 6 weeks ±1 week up to approximately 24 months (cycle 35) and then as per local clinical practice.
Other Clinical Assessments			
Adverse Events	X	X	
Concomitant medications and non-drug supportive interventions	X		All concomitant medications and non-drug supportive interventions should be recorded in the CRF until the participant has completed 35 cycles of treatment (approximately 24 months). After cycle 35 the data will be reported in the medical chart, but not collected in the CRF.

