# 9.4.2. Safety Analyses

All safety analyses will be performed on the Safety Population.

Drug exposure will be summarized using descriptive statistics.

All AEs will be coded using the Medical Dictionary for Regulatory Activities (MedDRA). The investigator will classify the severity of AEs using the CTCAE v4.03. A treatment emergent AE (TEAE) is defined as any event that occurs for the first time during the on-treatment period or AEs that were observed prior to the start of study treatment but increased in severity during the on-treatment period. Only TEAEs with an onset date prior to date of last dose + 28 days or the date of initiation of a new anti-cancer therapy (whichever occurs first) will be tabulated in summary tables. All data will be listed. The number and percentage of participants with AEs will be summarized by MedDRA system organ class, preferred term, relationship to study intervention, and severity. A byparticipant listing will be provided for those participants who experience an SAE, including death, or experience an AE associated with discontinuation of study intervention.

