5.2.3. Definition of Cycle and Cycle Day

Cycle start and end dates are derived per patient. Treatment will be dispensed at the beginning of every 21-day cycle.

DMB02-GSOP-RF02 4.0 Statistical Analysis Plan Template 01-Nov-2018 PFIZER CONFIDENTIAL Page 16 TMF Doc ID: 98.03

- For Cycle X, the actual cycle start date for each subject is the earliest start date of dosing (dose>0 at that visit) in Cycle X visit CRF exposure page
- For all but the last cycle,
 - actual cycle stop date is calculated as the start date of the next cycle minus one day.
 - actual cycle duration is calculated from Day 1 of a cycle to the day prior to Day 1 of the next cycle, as follows: Actual Cycle Duration (weeks) = (cycle stop date cycle start date + 1) / 7
- For the last cycle, actual cycle duration is calculated as follows:
 - Actual Cycle Duration (weeks) = (last date of study treatment- cycle start date + 1) /7

The cycle day will be calculated as:

• Cycle day = Date of the assessment/event – cycle start date + 1.

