5.3.1. Missing Dates

For purposes of data listings, dates will reflect only the information provided by the investigator on the CRF.

DMB02-GSOP-RF02 4.0 Statistical Analysis Plan Template 01-Nov-2018 PFIZER CONFIDENTIAL Page 20 TMF Doc ID: 98.03 If start dates for adverse events or concomitant medications are completely missing, a worstcase approach will be taken whereby the events will be considered treatment emergent and the medications will be considered concomitant. If only partial information is available (e.g. only a month and year or only a year), and the partial information provides sufficient information to indicate the dates are prior to the start of study treatment (e.g. month/year less than month/year of first dose), then these will be considered to have started prior to treatment; otherwise a similar worst case approach will apply and these will be considered to have started after treatment.

Date of Last Dose of Study Treatment

No imputation will be done for first dose date. Date of last dose of study treatment, if unknown or partially unknown, will be imputed as follows:

- If the last date of study treatment is completely missing and there is no End of Treatment (EOT) CRF page and no death date, the participant should be considered to be ongoing and use the data cutoff date for the analysis as the last dosing date; or
- If the last date of study treatment is completely or partially missing and there is EITHER an EOT CRF page OR a death date available (on or prior to the data cutoff date), then impute this date as the last dose date:

= 31DECYYYY, if only Year is available and Year < Year of min (EOT date, death date),

= Last day of the month, if both Year and Month are available and Year = Year of min (EOT date, death date) and Month < the month of min (EOT date, death date), or

= min (EOT date, death date), for all other cases.

Missing or Partial Death Dates

Missing or partial death dates will be imputed based on the last contact date:

- If the entire date is missing it will be imputed as the day after the date of last contact (see derivation of date of last contact in section 5.2.4); or
- If the day or month is missing, death will be imputed to the maximum of the full (nonimputed) day after the date of last contact and the following:
 - Missing day: 1st day of the month and year of death, or
 - Missing day and month: January 1st of the year of death.

Date of Start of New Anti-cancer Therapy

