Anti-cancer therapies will be collected in short term follow up only (up to 35 days after treatment discontinuation)

Incomplete dates for new anti-cancer therapy will be imputed as follows and will be used to determine censoring dates for efficacy analyses:

- The end date of new anti-cancer therapy will be included in the imputation for start date of new anti-cancer therapy. If the end data of new anti-cancer therapy is:
 - completely missing then it will be ignored in the imputations below,
 - partially missing with only year available then the imputations below will consider 31DECYYYY as the end date of the new anti-cancer therapy, or
 - partially missing with only month and year available then the imputations below will consider the last day of the month for MMMYYYY as the end date of the new anti-cancer therapy.
- For participants who have not discontinued study treatment at the time of the data cutoff date, last dose of study treatment is set to the data cutoff date in the imputations below.
- If the start date of new anti-cancer therapy is completely or partially missing then the imputed start date of new anti-cancer therapy is:

= 31DECYYYY, if only Year is available and Year < Year of min [max (PD date + 1, last dose of study treatment + 1), end date of new anti-cancer therapy]

= Last day of the month, if both Year and Month are available and

Year = Year of min [max (PD date + 1, last dose of study treatment + 1), end date of new anti-cancer therapy]

Month < Month of min [max (PD date + 1 day, last dose of study treatment + 1 day), end date of new anti-cancer therapy]

= min [max (PD date + 1, last dose of study treatment + 1), end date of new anticancer therapy], for all other cases.

AE Onset Date

The following imputation rules apply if the event is unique for a participant or it is the first of a series of similar events; otherwise, the AE Onset Date will not be imputed:

- If the AE Collection Date is not missing, is less than the Date of First Exposure to Treatment, and is less than the AE Stop Date, then AE Onset Date is set to the Date of AE Collection.
- If the Previous Visit Date is greater than the Date of First Exposure to Treatment and less than the AE Stop Date, the AE Start Date is set to the previous visit date. DMB02-GSOP-RF02 4.0 Statistical Analysis Plan Template 01-Nov-2018 PFIZER CONFIDENTIAL Page 22 TMF Doc ID: 98.03

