- If the Date of First Exposure to Treatment is greater than the previous visit date and less than the AE Stop Date, the AE Onset Date is set to the Date of First Exposure to Treatment.
- Otherwise AE Onset date is set to the AE Stop date.

AE Stop Date

Ongoing events will have the AE Stop Date set to one of the following values:

- Date of Death, if the participant died and a date of death exists.
- Maximum of (Participant Withdrawal date, AE Onset Date, AE Collection Date) if the participant withdrew from the study and a date of withdrawal exists.
- Maximum of (AE Onset Date, Subject Summary Collection Date, AE Collection Date) if the Subject Summary CRF page exists but a date of withdraw does not exists.
- Maximum of (Last Treatment Date, AE Onset Date) if no Subject Summary page exits.

Imputation will only occur if event is unique for the participant, or it is the last of a series of similar events; otherwise the Stop Date will not be imputed. Adverse Events are deemed similar if they have the same verbatim term.

Resolved events will have the AE Stop Date set to the maximum of the AE collection date and the AE Onset date.

Other Missing or Partial Dates

Imputation methods for other partial dates are as follows:

- If the day of the month is missing for a start date used in a calculation, the first day of the month will be used to replace the missing date.
- If both the day and month are missing, the first day of the year is used.
- For stop dates, the last day of the month, or last day of the year is used if the day or day and month are missing, respectively.
- If the date is completely missing, no imputation will be performed.

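### The SAP's AE-onset imputation rules omit the case where the previous visit falls on the first-dose day, so onset is set to the stop date instead of the first-dose date

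*SAP*

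**What the plan says.** SAP 5.3.1 (AE Onset Date) limits its scope: "The following imputation rules apply if the event is unique for a participant or it is the first of a series of similar events". Four rules follow.

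1. If the collection date precedes both the first dose and the stop date, onset is the collection date.
2. "If the Previous Visit Date is greater than the Date of First Exposure to Treatment and less than the AE Stop Date", onset is the previous visit date.
3. "If the Date of First Exposure to Treatment is greater than the previous visit date and less than the AE Stop Date", onset is the first-dose date.
4. "Otherwise AE Onset date is set to the AE Stop date".

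The next part of the section imputes stop dates. For an ongoing event the stop date is the death date, or a maximum that includes the withdrawal date or the Subject Summary collection date, or, with no Subject Summary page, the later of last treatment and onset. For a resolved event it is the later of collection and onset.

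Three other statements bear on the result:

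- Earlier in SAP 5.3.1, for a completely missing start date, "a worstcase approach will be taken whereby the events will be considered treatment emergent".
- SAP 3.5.1 defines treatment emergence by a lower bound only (onset on or after treatment start). It lists without summarizing events collected outside the on-treatment period.
- Protocol 9.4.2 sets an onset-based upper limit: "Only TEAEs with an onset date prior to date of last dose + 28 days", or before new anti-cancer therapy if that comes first.

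**The concern.** Rules 2 and 3 are both strict inequalities, in opposite directions. A previous visit on the first-dose day satisfies neither, and rule 1 does not apply to an event collected after dosing. The fallback therefore dates the event at its end.

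This is not an unusual configuration. Under SAP 5.2.3 "the actual cycle start date for each subject is the earliest start date of dosing", so Cycle 1 starts on the first-dose day, and protocol 1.3.1 schedules a visit on Cycle 1 Day 1. An event reported at the next visit, with a missing onset, will normally have the two dates equal.

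At stake is the onset date of early events and, in some cases, their place in the safety tables. The stop date can itself be imputed and may lie well after treatment, whereas the protocol's tabulation limit depends on onset. Adverse events are the main safety endpoint of the study.

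**Working it through.** The plan gives no figure here, so the check is one of logic, with illustrative days.

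**Inputs.** First dose = Day 1. The event is collected on Day 43, the first day of Cycle 3 (2 × 21 + 1 = 43). That this is the next visit is an assumption drawn from the every-other-cycle schedule in protocol 1.3.2. The previous visit is Day 0, 1 or 2, the range allowed by the ±1 day window in protocol 1.3.1. Stop dates are varied.

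**Imputed onset under the four rules, in order and as written:**

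| Stop date | Previous visit Day 0 | Previous visit Day 1 | Previous visit Day 2 |
|---|---|---|---|
| Day 10 | Day 1 (rule 3) | Day 10 (rule 4) | Day 2 (rule 2) |
| Day 30 | Day 1 (rule 3) | Day 30 (rule 4) | Day 2 (rule 2) |
| Day 43 | Day 1 (rule 3) | Day 43 (rule 4) | Day 2 (rule 2) |
| Day 60 | Day 1 (rule 3) | Day 60 (rule 4) | Day 2 (rule 2) |
| Day 200 | Day 1 (rule 3) | Day 200 (rule 4) | Day 2 (rule 2) |

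Only the middle column follows the stop date. Nothing about the participant explains the difference between the columns.

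**Treatment-emergent status.** Over stop dates from Day 1 to Day 440 with the previous visit on Day 1, no imputed onset precedes Day 1. None fails the lower bound in SAP 3.5.1.

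**Tabulation.** Protocol 9.4.2 requires onset < last dose + 28 days. With onset = stop date, an event is excluded when stop ≥ last dose + 28:

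- last dose Day 30: stop on or after Day 58
- last dose Day 120: stop on or after Day 148
- last dose Day 400: stop on or after Day 428

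A stop date on or after the start of new anti-cancer therapy has the same effect.

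As an example, take an ongoing event collected on Day 43, last dose on Day 120 and death on Day 150. The imputed stop date is the date of death, so onset = Day 150. That is 150 − 120 = 30 days after the last dose and past the Day 148 limit, although the event was known by Day 43. The death branch does not use onset, so this result needs no assumption about the order of imputation. The withdrawal, Subject Summary and resolved-event branches do use onset, while the onset rules use the stop date. The SAP gives no order of evaluation for them.

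**After the change.** With rule 2 inclusive, a previous visit on Day 1 gives onset Day 1 for every stop date after Day 1. No event then crosses the limit, and the Day 0 and Day 2 columns do not change.

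**The case against.** A reader might infer that everything reported at the first on-treatment visit is affected, or that early events lose treatment-emergent status. The documents support neither. The rules touch only events whose onset needs imputing and that are unique or first in a series. A later onset cannot fail a lower bound, and the worst-case rule separately protects events with a completely missing start date.

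Other limits also stand:

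- **Previous visit is undefined.** Protocol 1.3 allows unplanned visits, protocol 8.2.5 calls for lipid checks at weeks 2, 4 and 8, protocol 8.2.2 describes monthly ECGs, and SAP 5.2.3 has drug dispensed every cycle. If any of these counts as a visit, rule 2 may already apply by Cycle 3. Equality would still arise at the first contact after Cycle 1 Day 1, but over a shorter interval.
- **Late stop dates are a subset.** SAP 2.2 describes follow-up of up to 35 days. Longer follow-up concerns participants who stop for reasons other than progression (protocol 1.3.3). With no Subject Summary page, an ongoing event stops at last treatment and stays tabulated.
- **The SAP wording may keep the event.** SAP 3.5.1 turns on when an event was collected. One collected on Day 43 during treatment could remain in the tables on that reading. Only the protocol's onset-based limit clearly removes it.
- **Misdating alone reaches few outputs.** The planned AE summaries are counts by term, grade, causality and action. No analysis of time to onset or duration is planned.

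These points narrow the consequence. They do not supply a rule for equal dates, and the worst-case rule addresses status without saying that it overrides the tabulation limit.

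**Conclusion.** Wrong as written, and minor. When the previous visit is the first-dose day, onset is set to the stop date where the first-dose date is plainly intended. Treatment-emergent status is not lost. Loss from the summary tables is conditional: it needs a reported or imputed stop date on or after last dose + 28 days or new anti-cancer therapy, and the protocol's limit rather than the collection-based reading of SAP 3.5.1.

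The documents give no rate of missing onset dates, so the number affected cannot be computed; it is probably small and could be zero. For scale, with 70 treated participants, one participant missing from a table row lowers that incidence by 1/70 = 1.4 percentage points. No efficacy result is involved. The conclusion assumes that Cycle 1 Day 1 is the last visit before the report and coincides with the first dose.

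**What to change.** In SAP 5.3.1:

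1. Make the first comparison in rule 2 inclusive (previous visit on or after first dose).
2. Evaluate the onset rules with the reported stop date only. Where none is reported, whether the event is ongoing or resolved, apply rules 2 and 3 without the stop-date condition (and rule 1 likewise, so that an event collected before dosing is not moved). Impute the stop date afterwards. This removes the circularity.
3. State that the worst-case rule in the same section governs both treatment-emergent status and inclusion in the summary tables, whatever the imputed onset.

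The cost is SAP wording and one programming condition before database lock. No data collection changes.

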5.3.2. Missing Toxicity Grade of Adverse Events

Prior to Study Treatment: If no toxicity grade is available or the grade is reported as unknown for an adverse event prior to the first study treatment, then Grade 1 will be assumed for purposes of defining a baseline grade.

DMB02-GSOP-RF02 4.0 Statistical Analysis Plan Template 01-Nov-2018 PFIZER CONFIDENTIAL Page 23 TMF Doc ID: 98.03 In summaries which present maximum toxicity grade, the maximum of non-missing grades will be displayed. Missing grade will only be displayed for cases where a participant reported only one event and the grade is missing.

6. ANALYSES AND SUMMARIES

6.1. Primary Endpoint

6.1.1. Confirmed OR by ICR

Analysis set: ITT: All enrolled participants who take at least 1 dose of Lorlatinib

Analysis methodology:

• Objective Response Rate (ORR) defined as the percentage of patients with a confirmed best overall response (BOR) of CR or PR according to RECIST v1.1

BOR will be determined based on reported overall responses at different evaluation timepoints by the independent radiologist from the date of treatment start until documented disease progression or start of new anti-cancer therapy, according to the following rules:

- CR = at least two determinations of CR at least 4 weeks apart and documented before progression and start of new anti-cancer therapy
- PR = at least two determinations of PR or better (and not qualifying for a CR) at least 4 weeks apart and before progression and start of new anti-cancer
- SD (for patients with at least one measurable lesion at baseline) = at least one SD assessment (or better and not qualifying for CR or PR) ≥ 6 weeks after date of treatment start and before progression and the start of new anti-cancer therapy
- Non-CR/Non-PD (for patients with only non-target disease at baseline) = at least one Non-CR/Non-PD assessment (or better and not qualifying for CR or PR) ≥ 6 weeks after date of treatment start and before progression and the start of new anti-cancer therapy
- PD = progression ≤ 14 weeks after date of treatment start and not qualifying for CR, PR or SD
- Not Evaluable (NE) = all other cases.

Clinical deterioration will not be considered as documented disease progression.

- patients without documented CR or PR will be considered as non-responders
- Exact CI for a binomial proportion for ORR using the Clopper-Pearson method
- best % changes vs baseline as defined below under Summaries used for Reporting DMB02-GSOP-RF02 4.0 Statistical Analysis Plan Template 01-Nov-2018 PFIZER CONFIDENTIAL Page 24 TMF Doc ID: 98.03

• % change vs baseline across visits as defined below under Summaries used for Reporting

Intercurrent events and missing data:

- data on response after subsequent anti-cancer therapy is administered will be excluded
- participants with death prior to first post-baseline assessment, inadequate baseline assessment, new anti-cancer therapy started prior to first post-baseline assessment, and all post-baseline disease assessments missing will also be considered as non-responders.

Summaries used for reporting:

- The frequency (number and percentage) of patients with BOR of CR, PR, SD, PD, non-CR/non-PD (applicable only to patients with non-measurable disease at baseline), and NE (not-evaluable)
- ORR estimated by dividing the number of patients with OR (CR or PR) by the number of patients in the ITT population
- corresponding exact 2-sided 95% CIs
- Waterfall plots of best %change vs baseline
 - A waterfall plot of maximum percent reduction in the sum of longest diameter for nonnodal lesions and short axis for nodal lesions from baseline will be created. These plots will display the best percentage change from baseline in the sum of the diameter of all target lesions for each patient with measurable disease at baseline and at least one valid post-baseline assessment. The best percent change from baseline will be calculated from start of study treatment up to first visit with disease progression or to the last visit available prior to the start of new anti-cancer therapy (for patients who start new antitumor therapy prior to progression or who are progression-free patients at the time of analysis)
- Spider Plots of %change from baseline across visits
 - A spider plot of %change from baseline across visits in the sum of longest diameter for non-nodal lesions and short axis for nodal lesions from baseline will be presented. These plots will display the % change from baseline in the sum of the diameter of all target lesions for each patient with measurable disease at baseline and at least one valid postbaseline assessment. The % change from baseline will be calculated from start of study treatment to each visit up to first visit with disease progression or to the last visit available prior to the start of new anti-tumor therapy (for patients who start new antitumor therapy prior to progression or who are progression-free patients at the time of analysis).

